#### 4.6A Packaging and Labeling

The drug will arrive at UC packaged by the manufacturer, Bedford Labs Inc. It will be prepared for use by our IDS group as will be the placebo control. The drugs will be labeled with a numeric code that will be unknown to the research team and the research subjects. The code will be included in the database with the volunteer data. The study will be unblinded after completing the Pilot program.

#### 4.7A Receipt of Drug Supplies

Caffeine is inexpensive and stable. The IDS group will be instructed to place an order sufficient for the entire Pilot Project and they will be required to store the drug. The placebo will be prepared as needed. It too should be stable for a period of time.

#### **4.8A Product Storage and Stability**

Caffeine is stable for months in the vials shipped by the manufacturer if stored at room temperature (15 – 30 degrees C). Caffeine is preservative free.

#### **4.9A Dispensing of Study Drug**

Caffeine or placebo will be injected via and intravenous line by one of the two attending anesthesiologists. Only a certified anesthesiologist will be allowed to dispense either the drug (caffeine citrate) or the IDS prepared placebo.

#### **4.10A Return or Destruction of Study Drug**

Any remaining caffeine will be discarded as will be any remaining saline.

### **5. STUDY PROCEDURES**

Each subject will attend 4 sessions to complete the study.

#### **5.1 Screening Session 1**

In the first screening session, an anesthesiologist will explain the purpose of the trial and carefully go over the consent form. If the subject is willing to enroll the consent form will be signed. Next, the anesthesiologist will take a detailed medical history and perform a physical examination of the subject. A baseline EKG and urine toxicology screen text will be obtained. If the subject meets the criteria for the study, the subject will be enrolled in the trial. At this point a pre-study training session will be provided to familiarize the subject with the psychomotor tests.

#### **5.2 Study sessions 2 – 3**

In the following two sessions, each subject will receive general anesthesia in one session (with a saline injection as a placebo control) and receive general anesthesia and caffeine citrate (15 mg/ kg equal to 7.5 mg/ kg of pure caffeine) in the other session in a randomized manner. For each subject, each session involving anesthesia will be at least 2 weeks apart.

For each session, subjects will be asked not to eat and drink 8 hours prior to the study in order to minimize the potential risk for aspiration during anesthesia. They will be asked to refrain from alcohol or drug use for 24 hours prior to the sessions. A toxicology screen will be used for each session. Once the subject is checked in, a peripheral intravenous catheter (IV) will be inserted on one of the arms by the anesthesiologist ([name], [name] or [name]). The IV is used to administer medications during the course of the study. After the IV insertion, American Society of Anesthesiologists (ASA) standard monitoring, including EKG, blood pressure (BP), respiratory rate, end tidal CO2, pulse

oximetry, BIS monitor and temperature, will be used to assess the subject (see below for further details). The subject will then be asked to breathe 100% O2 via a facemask for two minutes. After the lungs are filled with 100% O2, the subject will be given propofol (2mg/kg), as an IV bolus, to induce anesthesia. Within 1-2 minutes, the subject will become unconscious. If the subject is still conscious, an extra dose of propofol (0.5 to 1 mg/kg) will be given until the subject is in a deeper stage of anesthesia. A Laryngeal Mask Airway (LMA), a rubber airway device, will be inserted via the mouth into the larynx. This device will help to optimize the patency of the airway while the subject is completely anesthetized. This allows the subject to breathe easier without the help of a ventilator. This is the induction phase of anesthesia. After induction, the subject will be given isoflurane (1.0 MAC, as adjusted by age and weight by the anesthesia machine) for 60 minutes. This period is called the maintenance phase of anesthesia. 60 minutes will ensure that each subject reaches anesthetic equilibrium. Oxygen flow will be kept at 2 L/min during the maintenance phase. Ten minutes before terminating the isoflurane, volunteers will be infused with a solution containing saline (control) or with caffeine (test). After the termination of isoflurane, the subject will be allowed to wake up. This phase is called the emergence phase of anesthesia. During the emergence phase, Oxygen flow will go up to 8 L/min to avoid rebreathing. We will test whether the caffeine shortens the emergence phase of anesthesia.

[EKG, respiratory rate, end tidal CO2, pulse oximetry and temperature are monitored continuously, once the volunteer is connected to the monitoring machines. A bispectral index (BIS) monitor, will continuously measure depth of anesthesia. Prior to starting the procedure, blood pressure will be measured every 5 minutes; this measurement of blood pressure will provide the baseline for subsequent BP measurements. Blood pressure will be measured every 2 minutes during the first 10 min of the anesthesia, which includes the induction period. BP will be measured every 5 min throughout the course of anesthesia and the first 30 min in the PACU. After that, BP will be measured every 10 min until the subject is discharged. This data is stored automatically for each patient in our hospital's Epic database].

Propofol is the preferred agent for the induction phase because it does not cause airway irritation. Additionally, propofol is normally used for anesthesia induction in human patients. There are several advantages to use isoflurane as the main anesthetic agent. Most importantly, it is an extremely safe anesthetic that has been used for decades. All our preliminary animal data was generated with isoflurane. Because it takes slightly longer to "wake up" from isoflurane anesthesia, compared to other volatile anesthetics like sevoflurane, it will allow us to better differentiate the actions of the caffeine. During this study, we do not plan to use other anesthetic agents, such as midazolam, fentanyl, and muscle relaxants to minimize the interactions of these drugs to our study drug. However, propofol and muscle relaxants are available at the bedside in case they are needed for the management of unexpected airway situations, such as laryngeal spasm. If an unexpected airway emergency occurs, the ASA difficult airway algorithm will be applied for airway management. The subject will be allowed to breathe spontaneously unless the tidal volume is less than 3 ml/kg. We will optimize the tidal volume at around 5 ml/kg to make sure each subject receives similar amount of isoflurane for an hour. Pressure support mode may be applied to optimize the tidal volume if necessary. The

study drug (caffeine citrate) or the placebo (saline) will be given intravenously 10 min before the end of 1 hour isoflurane anesthesia. The anesthesiologists will be blinded to the medication injected to the subject since the pharmacists in the IDS GROUP prepare the drug or the placebo control. When isoflurane is turned off, the subject will eliminate isoflurane passively via breathing. We will measure the time between when the isoflurane is stopped to the awakening of the subject. We will record the time to recovery of the gag reflex, until the subject's eyes open, until the subject's mouth opens, and the time until the subject can respond to the command to grip the hand of the attending physician and the removal of the laryngeal mask. After the subject is awake and relatively alert, he will perform psychomotor tests to measure his cognitive function. The subject will be required to complete a simple set of cognitive tests to determine if they are still impaired by anesthetic. Both "control" and test subjects will be required to complete the same tests. In total there are 3 different tests. The tests will be repeated every 15 minutes in order to obtain a recovery time course.

There will be at least two anesthesiologists present during the entire period of anesthesia. Each subject will be given a dose of antiemetic medication, zofran (4 mg) 20 minutes before the end of the anesthesia to minimize the incidence of post anesthesia nausea and vomiting. During the period of anesthesia, we will keep the subject's BP within 20% of its pre-anesthesia value. If the BP falls more than 20% of the baseline, for more than 5 minutes, we will first give IV fluid to replete the fluid deficit due to the restriction of fluid intake prior to the study. Vasoactive medications will be given if necessary.

One hour after the isoflurane is stopped, if the subject is awake, oriented and showing stable vital signs, one of the anesthesiologists may leave the room to prepare for the afternoon session. There will always be at least one anesthesiologist with the test subject at all times. Most of the time there will be two anesthesiologists.

At the conclusion of the study, we will discharge the subject based on the criteria used in our post anesthesia care unit in the hospitals. In general, the subject should be awake and alert with the stable vital signs. He should be able to drink clear liquid, void and ambulate before discharge home. We will call a car service for him without cost to the subject. The subject will be expected to live within 30 miles of The University of Chicago to make sessions easily accessible. Upon discharge, the subject will be required to be accompanied by a responsible adult. Each session for any given subject will be at least 2 weeks apart. The total time of each session, including the pre-anesthesia preparation, testing and recovery from anesthesia, will be ~4 hours. We will call the subject on the same day and the next day after each session to make sure the subject fully recovers without any adverse event. The subject will get another call a week after the procedure.

Subjects will be tested in this manner a total of two times. In one of the tests they will be anesthetized with isoflurane and injected with a saline solution and in one test they will be anesthetized with isoflurane and then injected with caffeine citrate (15 mg/ kg).

After terminating anesthesia, the subject will perform psychomotor tests to measure his cognitive function. The subject will be required to complete a simple set of cognitive tests to determine if they are still impaired by anesthetic. Both "control" (saline injection) and test subjects (those that obtain caffeine) will be required to complete the same tests.

Memory will be tested with 20 words, after which the subject will be asked to recall the words, order not being important. Two hours later the subject will be asked for the same words. The Digit Symbol Substitution Test asks subjects to substitute symbols for numbers for 60 seconds. Each time there will be different symbol number codes. The subjects will also be asked to estimate a period of time, typically 30 seconds. Blood pressures, heart rate and O2 saturation will be monitored. The entire suite of tests will be repeated two hours later. This latter test will allow us to assess whether the drugs allow recovery of cognitive ability.

**\*Please note:** We may recruit one or two additional anesthesiologists to our team. We will only recruit attending clinicians. They would take all the human clinical trial coursework and then we would have training sessions related to our protocol. The IRB should be aware that our protocol was designed to be as similar as possible to a standard surgical session with anesthesia, so that our research protocol will be instantly familiar to any experienced anesthesiologist.

Schema:

Procedure	Screening Session 1	Study Session 1	Study Session 2
Time	1 week prior to study	Start of Study: week 0	Week 2-4
Explain Trial to subject Obtain Consent	X		
Medical History	X		
Physical exam	X		
Vital signs	X	X	X
EKG	X	X	X
Urine Toxicology screen	X	X	X
Enroll Subject in Trial	X		
Psychomotor Training session	X		
Propofol Induction – Isoflurane maintenance		X	X
**Saline Control injection		X	
**caffeine (15 mg/ kg) injection			X
Psychomotor session 1 + 2		X	X
Adverse Event report		X	X

\*\*Please note that the drugs will be applied in a double-blind manner and will be prepared by a hospital pharmacist.

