There are cognitive impairments that last for hours following anesthesia (Nathanson *et al.*, 1995; Larsen *et al.*, 2000; Chen *et al.*, 2001). Reaction times and memory are impaired following anesthesia (Nathanson *et al.*, 1995; Larsen *et al.*, 2000; Chen *et al.*, 2001). Outpatients are being released from surgery/ anesthesia on an ever shortening time scale to save money. It would be significant if clinicians could wake the patients safely, rapidly and completely with no cognitive issues. The psychomotor studies will allow us to assess whether caffeine helps ameliorate the cognitive problems associated with anesthesia. Subjects will be required to carry out a series of simple psychomotor tests thirty minutes after anesthesia and then again two hours later. By comparing results, memory and reaction times we will determine whether Caffeine helps ameliorate cognitive problems, relative to the saline treated controls. Data from each test will be analyzed and plotted separately.

Part 2: Up to 8 additional healthy human males will be recruited for this part of the study. If the effects of caffeine in humans mirror that of the rat, we will need ~8 more volunteers to complete the trial assuming that each volunteer attends all 4 anesthesia sessions. We anticipate some dropout. This is the part we are asking for permission to start.

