## **8. SAFETY AND ADVERSE EVENTS**

### **8.1 Safety**

Prior to induction of anesthesia and throughout the application of anesthetic, up until the anesthetic is discontinued and the subject opens their eyes, there will be two anesthesiologists with each subject continuously. After waking, there will be an

anesthesiologist present for the next 2 hours until the subject is released and the second anesthesiologist will be present for the first hour of recovery and then available but not necessarily in the room afterwards.

The exclusion criteria will eliminate any subject with high risks for this study. The study will be carried out adjacent to the adult operating rooms that are fully equipped with monitors, resuscitation equipment, oxygen, suction, airway and cardiac code carts etc.

Note that having two accredited anesthesiologists present throughout the anesthesia is a standard higher than that used in a typical operating room. This is done to minimize risk. If we can use each subject as their own control, that will lead to the fewest total number of anesthetics due to reduced population variance.

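### Cognitive secondary endpoint: an open-ended 15-minute test series is not reconciled with a two-battery schedule, and reaction time and limb motor control have no described score

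*Combined protocol and SAP*

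**What the plan says.** Cognitive recovery is a secondary objective in the Study Summary and in 1.2. Section 2.8 says the tests will cover reaction times, memory and motor control in the sense of limb movement, and that details follow.

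The details are in 5.2, which gives two schedules. The paragraph on emergence starts the tests when the subject is awake and alert enough, says there are three of them, and adds: "The tests will be repeated every 15 minutes in order to obtain a recovery time course". It gives no number of repeats, no stopping time and no analysis. Later in 5.2 the tests are described as recall of 20 words, a 60-second Digit Symbol Substitution Test and time estimation ("The subjects will also be asked to estimate a period of time, typically 30 seconds"). There the repeat is a single one: "The entire suite of tests will be repeated two hours later". For the word list, "Two hours later the subject will be asked for the same words". For the digit-symbol test, "Each time there will be different symbol number codes".

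Section 6.2 gives clock times: "Subjects will be required to carry out a series of simple psychomotor tests thirty minutes after anesthesia and then again two hours later". It promises a comparison of memory and reaction times and says only that each test gets its own analysis and plot. The schema at the end of 5.2 lists "Psychomotor session 1 + 2".

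**The concern.** There are two separate problems.

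The first is the schedule. Staff who follow one paragraph of 5.2 and staff who follow another, or 6.2, could collect different data. If the series is run, 6.2 does not say what is done with the extra time points, so the choice of comparison stays open until after unblinding. The series is also anchored to waking, which is the very thing caffeine is hypothesized to alter. A subject who wakes sooner in one session would be tested sooner after isoflurane-off in that session, so treatment and elapsed time would be mixed in the within-subject comparison.

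The second is the outcome list. A comparison of reaction times is announced in 6.2, and limb motor control in 2.8, yet no test is described as producing either score. With at most 8 pairs, inconsistent or missing measurements cannot be repaired afterwards.

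**Working it through.** The plan states no sample size, power or significance level for the cognitive endpoint, so there is no design figure to reproduce. The check is a comparison of the texts plus some counting.

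**1. The schedules side by side**

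| Place | Start | Repeats | End |
|---|---|---|---|
| 5.2, emergence paragraph | a state (awake, alert enough) | every 15 min | not stated |
| 5.2, description of the tests | after anesthesia, no clock time | one, two hours later | second battery |
| 6.2 | 30 min after anesthesia | one, two hours later | 120 or 150 min |
| Schema | not timed | two sessions named | not stated |

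**2. Two readings of 6.2** (anesthesia taken to end at isoflurane-off)

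- Two hours counted from the first battery: 30 + 120 = 150 min.
- Two hours counted from the end of anesthesia: 120 min. The batteries are then 120 − 30 = 90 min apart, which does not match the two-hour repeat in 5.2.

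**3. Batteries per session.** For a 15-minute series, n = (end − start)/15 + 1. The spans below are assumptions, because the plan gives none.

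- 30 to 120 min: 90/15 + 1 = 7 batteries, 7 × 3 = 21 test results.
- 30 to 150 min: 120/15 + 1 = 9 batteries, 27 results.
- 0 to 150 min: 150/15 + 1 = 11 batteries, 33 results.
- Two-battery schedule: 2 batteries, 2 × 3 = 6 results.

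The ratio is 7/2 = 3.5 to 11/2 = 5.5. In the 30-to-150 case the series contains both batteries of 6.2, and the other 9 − 2 = 7 have no stated analysis.

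**4. Effect of starting at waking.** If testing starts w minutes after isoflurane-off, battery k falls at w + 15(k − 1). For one subject's two sessions, the difference in elapsed time at every battery is the difference in w. With assumed starts of 5 and 15 min, the batteries fall at 5, 20, 35, … and 15, 30, 45, …, a shift of 10 min throughout. On a clock fixed to isoflurane-off the shift is 0.

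**5. The word list.** Section 5.2 specifies new codes for the digit-symbol test but the same words for the two-hour recall. It does not say whether those words are asked for in between. For a 30-to-150 series, the extra recalls before the delayed one are 0 if they are not re-tested and 7 if they are asked for at every intermediate point.

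**6. Promised domains against described tests**

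| Promised | Where | Test described as scoring it |
|---|---|---|
| Memory | 2.8, 6.2 | 20-word recall |
| Reaction time | 2.8, 6.2 | none |
| Limb motor control | 2.8 | none |

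One of three promised domains has a described measure. None of the three tests is described as giving a reaction-time or limb-movement score.

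**The case against.** The schedules may be nested: a 15-minute series from 30 to 150 minutes would include both batteries. That is possible, but no section says so, and 6.2 gives the other points no role.

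The clock times in 6.2 stand between the Part 1 (pilot) text and the Part 2 heading, so they may be carried over from the pilot. This is a fair caution against treating them as settled, and a further reason to state the schedule afresh. The schema row is weak evidence too. Its columns are Study Session 1 and Study Session 2, so it may mean only that testing happens on both anesthesia days. The conflict does not need it, because 5.2 and 6.2 already supply it.

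Digit-symbol substitution is timed and done by hand, so the domain names may be loose labels. That stands in part: the test reflects psychomotor speed indirectly. It is still not described as scoring reaction time or limb movement.

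A reader might also infer that the second battery would be lost because the subject has already gone home, since 8.1 has an "anesthesiologist present for the next 2 hours until the subject is released". The documents do not support this. Section 3.12 puts completion of the psychomotor tests before release, 2.9 and 5.2 discharge on criteria, and 8.1 describes staffing. Nor do they support saying that the delayed recall is contaminated by rehearsal: whether the words are re-tested is simply not stated.

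**Conclusion.** The concern holds in two parts. The cognitive endpoint has an open-ended 15-minute series and a two-battery schedule that are not reconciled. Reaction time (2.8, 6.2) and limb motor control (2.8) are promised without a described measure. The difference is 2 batteries per session against 7 to 11, but the upper figures rest on assumed spans; as written, the length of the series is undefined. The size of the shift in test times between sessions depends on waking times that the plan does not give.

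This should be corrected because it determines what the secondary objective can conclude. It does not make the whole cognitive comparison impossible: word recall, digit-symbol performance and time estimates can all be compared once the timing is fixed. The primary endpoint is unaffected. The statement that no score is described rests mainly on 2.8, 5.2 and 6.2. Some pages of the pilot-data section (1.1.4) and of section 4 could not be checked.

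**What to change.** State one schedule in 2.8, 5.2, 6.2 and the schema. Time it from isoflurane-off, make it identical in both sessions, and use waking only as a condition of readiness. Say whether the second battery comes two hours after the first or two hours after anesthesia.

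If the 15-minute series is kept, give it an end, leave the delayed-recall words out of it, and put its analysis in 6.2.

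Restate the outcomes in 2.8 and 6.2 as the scores actually taken: words recalled immediately and at two hours, digit-symbol score in 60 seconds, and error in the time estimate. Relabel or drop the reaction-time and limb-motor claims; keeping them as aims would need an added, scored test.

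The cost is mainly wording, plus a check against the session of about 4 hours in 2.4. Isoflurane plus the wait for the second battery takes 60 + 120 = 180 or 60 + 150 = 210 of about 240 minutes, before preparation, induction and the battery itself. There are three downsides. The recovery time course is lost if the series is dropped. The two unmeasured aims are given up if their claims are dropped. A subject who cannot be tested at a scheduled time leaves a missing value among at most 8 pairs.

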**6. STATISTICAL PLAN AND CONSIDERATIONS**

**6.1 Sample Size Determination**

Members of the IRB should understand that the sample size described above is an estimate, since we could not find good data on human “waking” times from isoflurane anesthesia in the literature. Thus we used our own animal studies to estimate sample size. There are at least three reasons why our sample size might be in error. First, rats are not people. They may get rid of isoflurane differently than do humans due to their higher respiration rates. In addition, rats are genetically more similar to each other than are humans. That would tend to increase human variance relative to that of the rat. On the other hand, the equipment used to anesthetize rats is less sophisticated than that in humans. In humans, the expired anesthetic concentration is measured, thereby allowing for precise anesthetic concentration, in the lungs. This is not possible in rats and so the anesthetic dose applied is less precise. This will tend to lower human variance. This is a long-winded way to say that our sample size estimate may be wrong. In these studies rats were used 4 times (twice with a saline injection twice with an injection of saline containing caffeine), a strategy that reduced variance.

Additional caveats: The 15 mg caffeine citrate that we propose is equivalent to 7.5 mg/kg of pure caffeine. We have never tested 7.5 mg/kg caffeine in rats, nor have we ever studied isoflurane at a concentration of 1 MAC.

We use the following stringent criteria to determine sample size: Power will be set to 95% and  $p \leq 0.01$ .

Rats waking from isoflurane anesthesia with 5 mg/kg caffeine (isoflurane ~ 1.5 MAC):  
(Control - saline injection) - Mean = 540 sec, SD = 159.04  
(Test - 5 mg/kg caffeine in saline injection) - Mean = 269.67 sec, SD = 103.69  
At this concentration of caffeine we would need  $n=12$  measurements for control and  $n=12$  measurements for caffeine to meet our stated stringent criteria. If each person were used for one control and one caffeine measurements we would need 12 people for the study.

We are using human volunteers twice, not four times like the rat population, we expect higher variance. Nonetheless, we expect 8 total volunteers will satisfy our study. This is because we are using a higher concentration of caffeine (7.5 mg/kg), which should produce a larger response than the 5 mg/kg shown above, and we will employ a lower concentration of isoflurane (1 MAC), which should be easier to antagonize.

